5.10 General data conventions

There is only one dose level for this study, as specified in the study protocol. Patients who deviate from the assigned dose and/or schedule will be clearly described in the CSR with regards to their treatment modification and if applicable in the list of protocol deviations (Section 5.4).

Continuous variables will be summarised and presented with summary statistics.

The median OS will be presented.

Categorical variables will be summarised in frequency tables. Percentages in the summary tables will be rounded and may therefore not always add up to exactly 100%.

The convention in Rave is that an unknown day resolves to 1st of the month and an unknown month resolves to January. Dates may be ordered by this; however, CRUK do not perform calculations on unknown dates except as stated below.

Durations of AEs: the start date of an AE is considered as Day 1 of the event and should be included in all duration calculations (i.e. if an AE starts and stops on same day, the duration should be reported as one day).

- For unrelated AEs, those with missing or partially completed end dates will not be excluded from analysis and the duration of the AE will be calculated from the first day of the month (if unknown) or first day of the year (based on RAVE conventions).
- For related AEs, prior to final data lock, an end date will be either i) confirmed AE end date or ii) stabilisation of AE. Cases where this is not possible are if the patient was lost to follow up. If lost to follow-up then the AE would stay as not recovered/not resolved. In this case duration would not be calculated.

Time to onset of AEs from IMP administration: the time to onset should be calculated from the date of the first AST-VAC2 vaccination and AEs occurring within a specific vaccination window (e.g. start date from date of 2nd vaccination to before date of 3rd vaccination) should also have times to onset calculated from the date of the last vaccination administered in that window (e.g. Vaccination 2). Onset time will be

calculated as 0 if the AE occurs on the same day as the dose; however, if the start time is missing, onset time will not be calculated (only applicable when the drug admin has a start time entered).

AE assignment: AE is assigned to the vaccination number it begins in. This is regardless of whether the AE start time shows the AE started before the dose that day. The only exception is for the first vaccination; if 'Did AE occur prior to first dose' is checked then no vaccination number will be assigned.

Duration of treatment: this is from the day of the first vaccination until the day of the final vaccination. Duration of treatment will be described using summary statistics.

Completed vaccination: AST-VAC2 vaccinations are to be given once a week for 6 weeks. A patient is considered to have completed vaccination when vaccination data entered is for each of those expected weekly visits (despite dose modifications).

Treated patients: If the drug administration form in the eCRF has the 'date of vaccination' completed, this constitutes a treated patient.

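### For unrelated AEs with a partial end date, the SAP's first-of-period rule gives durations that are zero, negative or too short, and it cannot be applied when the end date is wholly missing.

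*SAP*

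**What the plan says.** Everything turns on SAP section 5.10, General data conventions.

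- The data-capture convention for partial dates is that "an unknown day resolves to 1st of the month and an unknown month resolves to January".
- The default is not to compute with such dates: "CRUK do not perform calculations on unknown dates except as stated below".
- For AE durations, "the start date of an AE is considered as Day 1 of the event and should be included in all duration calculations". The worked case is that "if an AE starts and stops on same day, the duration should be reported as one day".
- An exception to the default follows: "For unrelated AEs, those with missing or partially completed end dates will not be excluded from analysis". For these events the SAP then fixes which date to use: "the duration of the AE will be calculated from the first day of the month (if unknown) or first day of the year".
- Related AEs have a different rule: "For related AEs, prior to final data lock, an end date will be either i) confirmed AE end date or ii) stabilisation of AE". If the patient is lost to follow-up, the event stays unresolved and "In this case duration would not be calculated".

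The section sets no lower limit at the AE start date. It gives no separate instruction for an end date with no day, month or year.

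**The concern.** Setting a partial end date to the first day of the month, or to 1 January, chooses the earliest date the event could have ended. Many AEs are short, so start and end often fall in the same month. The imputed end then precedes the start, and the formula returns a value that cannot be a duration. Where it does return a plausible value, that value is biased in one direction.

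Missing ends are foreseeable for exactly the events the rule covers. After the End of Vaccination visit, Protocol sections 7.3.2 and 9.3.3 collect only vaccine-related AEs, and footnote j of the schedule in Protocol section 7.5 limits monthly follow-up to drug-related events. An unrelated AE still present at that visit may therefore never acquire an end date, yet the SAP says its duration will be calculated.

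At stake is the reliability of any AE duration shown in a listing or descriptive summary. In a trial of about eight patients, one negative value would be conspicuous and could distort a summary. A programmer following the text would either output impossible values or improvise a rule that is not in the plan.

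**Working it through.** **Inputs.** The Day 1 convention, the same-day example and the first-of-period rule come from SAP section 5.10. The documents contain no AE dates, so all event dates and true durations below are assumptions for illustration.

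**Formula.** Duration = end - start + 1. For a partial end date, end = first of the known month (day unknown) or 1 January of the known year (day and month unknown).

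**The SAP's own figure.** Start and end on the same day: 0 + 1 = 1 day. This reproduces, and it is the smallest duration the convention allows.

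**Start and end in the same period.**
- Start 15 May, end day unknown in May: (1 May - 15 May) + 1 = -14 + 1 = -13 days.
- Start 15 March, end month unknown, same non-leap year: (1 January - 15 March) + 1 = -73 + 1 = -72 days.
- Start on the 2nd, end day unknown in that month: -1 + 1 = 0 days.
- Start on the 1st, end day unknown in that month: 0 + 1 = 1 day. The imputed end equals the start and does not precede it.

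**Full examples (assumed dates).**

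| Event | True days | Day unknown | Day and month unknown |
|---|---|---|---|
| 10 to 20 March 2021 | 11 | -8 | -67 |
| 1 to 20 March 2021 | 20 | 1 | -58 |
| 25 March to 10 April 2021 | 17 | 8 | -82 |
| 20 December 2020 to 10 February 2021 | 53 | 44 | 13 |

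The last two rows show that once the event has crossed into a later month (or year), the value is positive but short.

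**How often, by length of event.** Taking every start date in 2021 as equally likely, the share of events with duration zero or less is:

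| True duration | Day unknown | Day and month unknown |
|---|---|---|
| 7 days | 77.0% | 98.1% |
| 14 days | 54.0% | 96.2% |
| 30 days | 1.9% | 91.8% |
| 60 days | 0% | 83.6% |

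The mean understatement is 14.7 days with the day unknown and 182 days with the month unknown, whatever the true length. The rule is exact only when the true end was the first of the period: 12/365 = 3.3% of end dates with the day unknown, 1/365 = 0.3% with the month unknown. It is never too long.

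**Wholly missing end date.** Both branches need at least a known year. With none, there is no date to insert and the formula has no value.

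**The case against.** The strongest reply is that little depends on AE duration. The primary endpoint (SAP section 2; Protocol section 3.1.1) is frequency, causality and severity grade. Treatment-emergent status comes from an onset tick-box (SAP section 5.7), so an imputed end date changes no count. Tables 8 to 12, the table list in SAP section 6.2 and the outcome measures in SAP section 7.5 contain no duration. It could appear in the AE listing, whose columns are not specified. AE review at each vaccination visit (Protocol section 7.2) and eCRF checks and queries (Protocol section 14.3) should also keep partial dates few. All of this stands, and it limits the consequence. It does not make the rule workable, because the SAP says that these durations will be calculated.

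A reader might draw four stronger inferences that the documents do not support:
- That the primary endpoint is compromised. Duration is not part of it.
- That a comparison of related with unrelated events is biased. The two groups do follow different rules, but no such duration comparison is planned.
- That the end always falls before the start. It does so only when the two share the unknown period and the event starts after its first day.
- That nearly all durations would be impossible. In a 30-day month, 29 of 30 start days (97%) do give zero or less, but only given an unrelated event, an unknown end day, and an end in the same month. It is not an error rate for the trial, and the documents do not say how many end dates will be partial.

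The phrase about calculating from the first day is loose and could be taken to mean a start date. The sentence is about end dates and cites the data-capture convention, so the reading used here is the natural one.

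**Conclusion.** The rule is wrong as written, within a narrow scope. It applies only to unrelated AEs whose end date is partial or missing. Within that scope, it contradicts the SAP's own one-day minimum when the event starts after the first day of the period in which it ends, and it understates duration otherwise unless the true end was the first day. It gives no answer for a wholly missing end date. The size for a single event runs from no error to a large negative value (-13 and -72 days in the simplest examples).

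The proportions in the working rest on assumed durations and evenly spread start dates. They describe how the rule behaves and do not predict this trial's data. The consequence is confined to AE durations in listings or descriptive summaries. The safety conclusions on frequency, causality and grade do not change.

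**What to change.** Replace the sentence for unrelated AEs in SAP section 5.10 with one of two rules.

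1. **Do not calculate.** Where the end date is partial or missing, report no duration. This is the SAP's own default for unknown dates, and it already does this for related AEs lost to follow-up. It is the simpler option; its cost is that some durations go unreported.
2. **Impute late and flag.** Use the last day of the known month, or 31 December of the known year, capped at the earliest of death, last contact and data cut-off, never earlier than the start date, and marked as imputed. The 15 May example then gives at most 31 - 15 + 1 = 17 days. The cost is that such values are upper bounds, and loose ones when the month is unknown: for a start on 10 March 2021, 31 December gives 365 - 69 + 1 = 297 days before capping.

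Under either rule, report a wholly missing end date as ongoing or not resolved, with no duration or as greater than x days at the last contact at which the event was recorded as continuing.

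The change is a sentence or two in the SAP and a few lines of SAS. It needs no new data collection.

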### 5.4 Duration of treatment

Treatment should continue so that the patient receives six vaccinations unless (a) the patient asks to be withdrawn, (b) there is evidence of disease progression (as per Immune-Related Response Criteria (irRC) given in [Appendix 3](#)), (c) the patient is experiencing unacceptable toxicity or (d) the investigator feels the patient should stop the vaccinations for any other reason. Other reasons are listed in [Section 11.0](#).

An End of Vaccination visit will be carried out 30 days post the last vaccination day. This visit will document any emerging AEs since the last vaccination. Adverse events present at this visit, attributed to AST-VAC2 (highly probably, probably or possibly related) will be followed up until resolution or stabilisation of these events (even if the patient starts another anti-tumour treatment).

If a patient terminates treatment prematurely, an End of Vaccination visit should be performed within 30 days of the last vaccination day or when the decision is taken to withdraw the patient from further vaccinations or the trial. These patients should also be asked to continue attending hospital for the 3, 6 and 12 month from first vaccination follow-up visits to provide blood samples for immune analysis (unless the patient withdraws consent from further follow up and participation in the trial or if the Sponsor advises that further sampling is not required).

Patients will be asked to attend follow up as per Section 7.4 until the end of trial (EoT) is declared. The 'End of Trial' will be declared when all patients have either withdrawn (see [Section 11.0](#)) from the trial or died, or the last patient has completed their final follow-up visit (5 years post the first vaccination), whichever is the latter.

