### 7.4 Follow-up

#### 7.4.1 3, 6, 9 and 12 months post first vaccination

##### Patients should undergo the following assessments:

- Research blood samples 3, 6 and 12 months (all +/-1 week) post the first vaccination.
- At the above time points, an evaluation of any AST-VAC2 related AEs will also be performed. Assessments can be performed as clinically indicated.
- A further AE evaluation should be performed at 9 months post the first vaccination also. This can be in the form of a phone call to the patient.
- Any concomitant medications relevant to AST-VAC2-related AEs should be recorded.

All new and ongoing AST-VAC2-related AEs should be followed up until resolution or stabilisation, even if the patient goes onto another anti-cancer treatment. SAEs considered related to AST-VAC2 are always reportable regardless of the time elapsed.

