### 9.3.4 Follow-up of AEs and SAEs

Follow-up of AEs with a causality of possible, probable or highly probable will continue until the events resolve, stabilise or the patient starts another anti-cancer therapy.

The Pharmacovigilance Department will make requests for further information on SAEs to the trial site at regular intervals. Requested follow-up information should be reported to the Pharmacovigilance Department in a timely manner and as soon as possible after receipt of the follow-up request. For fatal or life-threatening cases, follow-up information must be reported to the Pharmacovigilance Department as soon as possible.

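### SAP 5.10 ends a related AE at stabilisation and leaves its duration blank after loss to follow-up, so durations of persisting related AEs can be too short or missing

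*SAP*

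**What the plan says.** **SAP 5.10, durations of AEs.** Counting is inclusive: "the start date of an AE is considered as Day 1 of the event and should be included in all duration calculations". For related AEs, before final data lock, "an end date will be either i) confirmed AE end date or ii) stabilisation of AE". Loss to follow-up is the only case named in which an end date cannot be given: "If lost to follow-up then the AE would stay as not recovered/not resolved", and "In this case duration would not be calculated".

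**Protocol, follow-up of related AEs.** The protocol uses stabilisation as a point at which follow-up may stop, and lists it separately from resolution:

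- Section 5.4: related AEs present at the End of Vaccination visit "will be followed up until resolution or stabilisation of these events", even if another anti-tumour treatment is started.
- Section 7.4.1: "All new and ongoing AST-VAC2-related AEs should be followed up until resolution or stabilisation, even if the patient goes onto another anti-cancer treatment".
- Section 9.3.4: follow-up "will continue until the events resolve, stabilise or the patient starts another anti-cancer therapy". Footnote j to the schedule of events (Section 7.5) also stops at new anti-cancer treatment.
- The AE row of the Section 7.5 schedule carries ongoing drug-related AEs to the end of extended follow-up. Sections 7.4.4 and 9.3.3 also continue to evaluate or collect ongoing related AEs, the latter until withdrawal, death or trial completion.

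**SAP 5.9, survival.** Censored survival times are shown with a '+' after the number of days.

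**The concern.** Stabilised is not resolved. The protocol treats stabilisation as a reason to stop chasing an event. The SAP makes it the date on which the event ends for the duration calculation. A related AE that plateaus and never clears is then given an end date and a closed duration, and any later observation of it is ignored for that purpose.

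The loss-to-follow-up rule discards information that is available: an event known to have lasted at least until last contact gets a blank.

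The error has a fixed direction. For an unresolved related AE, the stated duration is too short or absent, never too long. This is a first-in-human, purely descriptive trial of about eight patients, with five-year follow-up because the product is an ATIMP. Listings and narratives carry much of the safety evidence, and a single persisting related event deserves a correct description.

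**Working it through.** The documents state no AE duration to reproduce. The check applies the SAP's own counting rule to an illustrative related AE that stabilises and never resolves.

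**Inputs from the documents**

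- Duration = end date − start date + 1 (SAP 5.10, start date as Day 1).
- Six weekly vaccinations from day 1, so the last is on day 1 + 5 × 7 = 36 (Protocol 5.2).
- End of Vaccination visit 30 days later, day 36 + 30 = 66, with a ±5-day window of 61 to 71 (Protocol 7.3.2).
- Two-year survival cut-off and five-year end of follow-up (Protocol 13.1 and 12).

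**Assumptions**

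- Onset on day 1 or day 36.
- Stabilisation recorded on day 66 or day 365.
- The AE is still present at 2 years (day 1 + 730 = 731) or 5 years (day 1 + 1,826 = 1,827).

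**Minimum durations if the event is treated as ongoing**

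- Onset day 1: 731 − 1 + 1 = 731 and 1,827 − 1 + 1 = 1,827 days.
- Onset day 36: 731 − 36 + 1 = 696 and 1,827 − 36 + 1 = 1,792 days.

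**Result**

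| Onset | Stabilised | SAP duration | At least, 2 y | SAP as share | At least, 5 y | SAP as share |
|---|---|---|---|---|---|---|
| 1 | 66 | 66 − 1 + 1 = 66 | 731 | 9.0% | 1,827 | 3.6% |
| 1 | 365 | 365 − 1 + 1 = 365 | 731 | 49.9% | 1,827 | 20.0% |
| 36 | 66 | 66 − 36 + 1 = 31 | 696 | 4.5% | 1,792 | 1.7% |
| 36 | 365 | 365 − 36 + 1 = 330 | 696 | 47.4% | 1,792 | 18.4% |

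**Loss to follow-up.** The SAP gives no value. A censored rule gives last contact − start + 1, marked '+'. With onset on day 1 and last contact on day 365 (assumed), that is 365+ days.

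**Where the value could appear.** SAP Tables 8-12, the table list in SAP 6.2 and the registry outcome measures in SAP 7.5 count episodes or patients by term, grade, seriousness, relatedness or vaccination number. None summarises AE duration. That leaves AE listings, narratives and the further safety analyses that SAP 5.6 allows. SAP 5.10 itself treats duration as a reported quantity, since its same-day example says what should be reported.

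**Cases the rule does not cover.** SAP 5.10 is silent on a related AE still open at death or at withdrawal, or when follow-up stops at new anti-cancer therapy. It refers only to final data lock, whereas the clinical study report is written at the two-year interim cut-off (SAP 5.14.4), when related AEs may be open.

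**The case against.** The strongest reply is that little rests on this convention.

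- **No planned summary uses AE duration, and the primary endpoint is frequency, causality and grade.** This stands. A stabilised or lost AE is still counted in full, with its worst grade and relatedness. A reader might infer that the primary endpoint is biased; the documents do not support that.
- **Irreversibility is not hidden.** This largely stands. A reader might infer that persisting toxicity is reported as resolved. For a lost patient the SAP explicitly keeps the AE as unresolved, so only its length is missing. For a stabilised AE the SAP sets an end date but does not say that the outcome is coded as recovered.
- **The rules need not act on the longest events.** This stands for loss to follow-up: an AE open at last contact may have begun shortly before.
- **The protocol itself allows follow-up to stop at stabilisation.** This stands in part. Where observation stops there, a minimum duration to last assessment gives the same number with a '+'. The mark still matters, because it separates an event that ended from one that did not. Under Protocol 7.4.4, 7.5 (AE row) and 9.3.3, later observations should exist, and the SAP rule would ignore them.
- **Clinically significant related autoimmunity is handled elsewhere.** This stands. It meets the criteria in Protocol 3.3.3, is reported as an SAE and is described under SAP 5.8.2. That does not correct the duration rule for it or for other persisting events.

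**Conclusion.** The duration rule is wrong for related AEs that stabilise without resolving, and it discards a usable minimum for patients lost to follow-up. The effect is confined to durations in listings, narratives and any added safety summary.

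The direction is certain; the size is not. Under the assumed dates the SAP rule gives 31 to 365 days, against at least 696-731 days at 2 years or 1,792-1,827 days at 5 years. Across the rows of the table the understatement runs from about 2-fold (731 / 365 = 2.0) to about 58-fold (1,792 / 31 = 57.8). No single ratio should be quoted as the size of the problem, and nothing in the documents shows that stabilisation would be recorded early. The longer figures also need a patient who is alive and observed at 2 or 5 years; Protocol 2.1.1 cites lung cancer survival of 32% at 1 year and 10% at 5 years.

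This deserves correction before reporting, but it does not threaten the main safety conclusions.

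**What to change.** In SAP 5.10:

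1. Give a related AE an end date only when resolution is confirmed.
2. Show a stabilised AE as 'ongoing (stabilised on date)', with a minimum duration to the last assessment marked '+', as SAP 5.9 does for censored survival.
3. Apply the same rule to related AEs open at loss to follow-up, death, withdrawal and the two-year interim cut-off.
4. Define stabilisation.

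The protocol's follow-up rules for related AEs must also be reconciled. Sections 5.4 and 7.4.1 run to resolution or stabilisation regardless of other treatment. Section 9.3.4 and footnote j of Section 7.5 also stop at new anti-cancer therapy. Section 7.4.4, the AE row of Section 7.5 and Section 9.3.3 continue through extended follow-up or to trial completion. Which rule should apply is for the sponsor and investigators.

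**Cost.** A change to SAP wording and to one derivation. Some durations become lower bounds. The eCRF fields are not shown, so it cannot be assumed that stabilisation and resolution dates are held separately; if one field holds both, a flag will be needed, with some data cleaning. No planned summary table changes.

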### 1.5 Trial treatment:

Patients will receive AST-VAC2 vaccinations, administered by id injection at six time points over a period of six weeks (Figure 1). An interval of 7 days (+/- 1 day) should occur between each of the vaccination days. Two intradermal injections (totalling  $1 \times 10^7$  cells of AST-VAC2) will be administered on each vaccination day. The target administered dose of vaccine is  $1 \times 10^7$  cells of AST-VAC2.

Figure 1. Summary of vaccinations and research sampling

\* Timings may change if vaccinations are stopped before the sixth vaccination

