#### 5.3.2 Dose delays & interruptions

If at the time of the next scheduled vaccination day, one or more adverse events (AEs) (excluding ISRs) related to the AST-VAC2 vaccine (highly probably, probably or possibly related) are still present, have not resolved to Grade  $\leq 1$  and are considered by the Investigator to be clinically significant and a clear contraindication to vaccination, the next vaccination day should be delayed for up to two weeks until the AE(s) have recovered to this level. In case of uncertainty, individual cases should be discussed with the Sponsor. Patients who require a dose interruption of greater than two weeks will be reviewed on a case by case basis to determine whether the patient should be withdrawn from the trial. The Sponsor will confirm whether an extended interruption is acceptable or if the patient should be withdrawn from further trial treatment.

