### 7.3 Evaluations after vaccination

#### 7.3.1 Two weeks post vaccination visit

Two weeks after the patient has received their last vaccination they should be assessed for:

- Adverse events since the last visit. The start and stop dates of the AE together with the relationship of the event to AST-VAC2 (and COVID-19 vaccination if applicable) must be recorded in the medical records. All AEs must be graded according to NCI CTCAE Version 4.02 and protocol specific ISR grading system (See [Section 9.0](#) for further details regarding AE reporting requirements and ISR grading system).
- Concomitant medications (details should be recorded in the medical records).
- Research bloods.
- [REDACTED]

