### 9.3.3 Eligible patients

For eligible patients, SAE and AE collection and monitoring will commence at the time the patient gives their written consent to participate in the trial by signing the main trial consent form and will continue until 30 days after the last vaccination (administration of IMP). From this time point until the patient withdraws, dies or completes the trial, new or ongoing AST-VAC2-related AEs will be collected (regardless of whether the patient goes on to other anti-cancer therapies).

Should an Investigator become aware of any AST-VAC2 -related SAEs after the patient has completed the protocol-mandated follow-up period (as specified above), these must also be reported to the Sponsor within the expedited timelines in Section 9.4.

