5.8.1 Additional safety tables

A table of ISR grade by vaccination number will be produced.

CRUKD/17/003 RAP Version: 2.0 09Mar2023 FINAL

Table 12: Summary of Injection Site Reactions by Grade and Vaccination Number (*Safety Population*)

ISR Grade	Vaccination number at onset						
	Total	1	2	3	4	5	6
1	N	N	N	N	N	N	N
2							
3							
4							
5							

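### Table 12 counts injection site reactions over unequal, partly open-ended windows and without the number vaccinated, so its columns are not directly comparable

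*SAP*

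**What the plan says.** - **Assignment rule.** SAP 5.10: "AE is assigned to the vaccination number it begins in". For time to onset, the same section illustrates a vaccination window as "start date from date of 2nd vaccination to before date of 3rd vaccination". It gives no end for the window of the last vaccination. An event starting on a vaccination day goes to that day's vaccination, even if it began before the dose.
- **The table.** SAP 5.8.1, Table 12 shows ISR grade by "Vaccination number at onset": a Total column and columns 1 to 6. Cells are plain counts, with no patients or days at risk.
- **Spacing of doses.** Protocol 1.5: "An interval of 7 days (+/- 1 day) should occur between each of the vaccination days". For unresolved related events other than ISRs, Protocol 5.3.2 says "the next vaccination day should be delayed for up to two weeks until the AE(s) have recovered to this level".
- **After the last dose.** Protocol 9.3.3 collects all AEs for 30 days. After that, until withdrawal, death or completion, "new or ongoing AST-VAC2-related AEs will be collected". The End of Vaccination visit is at 30 days, plus or minus 5 (Protocol 7.3.2).
- **Numbers.** Up to eight patients, each receiving at most six vaccinations (Protocol 1.6 and 2.5.1). No formal statistical analysis is planned (SAP section 3, Table 1).

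**The concern.** Injection site inflammation is the principal potential toxicity named in Protocol 3.3.1, and a related Grade 3 or 4 ISR triggers independent review under Protocol 3.3.3. Table 12 is the only planned summary of ISRs by dose number; the ISR outcome measure in SAP 7.5.2 is by grade alone. A reader will look across columns 1 to 6 to see whether reactions to an allogeneic cell product build up or fade with repeated dosing.

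The columns do not measure the same thing. An earlier vaccination's window closes when the next dose is given, whereas a patient's last window stays open. For a patient who stops after vaccination 3, the long window falls in column 3. If fewer patients reach the later vaccinations, those columns also contain fewer people, and the table does not show it. With at most eight patients, one or two events in a different column can change the apparent pattern.

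**Working it through.** The plan states no figure for Table 12, so there is none to reproduce. The check has two parts.

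**1. Window lengths**

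- Between doses on schedule: 7 days (6 to 8).
- After a patient's last dose, to the End of Vaccination visit: 30 days (25 to 35).
- Ratio: 30/7 = 4.3. Extremes: 25/8 = 3.1 and 35/6 = 5.8. It is higher if related events after the visit are counted.
- Against an interval delayed by two weeks: 30/(7 + 14) = 30/21 = 1.4.

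**2. How much of this reaches the counts**

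The ratio carries over in full only if ISRs start at a constant daily rate and every patient completes. Reactions tied to the injection behave differently, so an illustrative model was used. All of the following are assumptions, not figures from the documents: one ISR per vaccination, exponential onset with mean *m* days after its own injection, 7-day windows before the last dose and 30 days after it, and assignment by onset date.

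If all 8 patients complete:

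- Column *c*, for *c* = 1 to 5: 8 × (1 − exp(−7*c*/*m*)).
- Column 6: 8 × (1 − exp(−30/*m*)) × Σ exp(−7*j*/*m*), with *j* from 0 to 5.

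For *m* = 7, columns 1 to 5 are 5.06, 6.92, 7.60, 7.85 and 7.95 (mean 7.08). Column 6 is 12.45, and 12.45/7.08 = 1.76. For *m* = 3, columns 1 to 5 are 7.22, 7.92, 7.99, 8.00 and 8.00 (mean 7.83). Column 6 is 8.86, and 8.86/7.83 = 1.13.

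The same calculation was run with an assumed drop-off of 8, 8, 8, 7, 6 and 5 patients at vaccinations 1 to 6, the long window following each patient's own last dose.

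| Mean onset *m* (days) | Column 6 / mean of 1–5, all complete | Column 6 / mean of 1–5, with drop-off |
|---|---|---|
| 1 | 1.00 | 0.68 |
| 2 | 1.04 | 0.70 |
| 3 | 1.13 | 0.76 |
| 5 | 1.42 | 0.94 |
| 7 | 1.76 | 1.14 |

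Under that drop-off, the patient-days behind the six columns are:

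- Columns 1 and 2: 8 × 7 = 56 each.
- Column 3: 7 × 7 + 30 = 79.
- Column 4: 6 × 7 + 30 = 72.
- Column 5: 5 × 7 + 30 = 65.
- Column 6: 5 × 30 = 150.

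The mean of columns 1 to 5 is 328/5 = 65.6, and 150/65.6 = 2.3, not 4.3.

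**Effect of a 7-day limit.** Column 6 becomes 8 × (1 − exp(−42/*m*)). With all patients completing, the ratio falls from 1.76 to 7.98/7.08 = 1.13 for *m* = 7 and from 1.13 to 8.00/7.83 = 1.02 for *m* = 3. It stays at 1.00 for *m* = 1. With drop-off, dividing each count by the number vaccinated gives 1.69 without the limit and 1.14 with it for *m* = 7, and 1.12 and 1.02 for *m* = 3. What remains is late reactions to earlier doses: columns 2 to 6 receive them and column 1 cannot.

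**The case against.** The strongest reply is that a longer window adds nothing unless reactions start late. If ISRs begin within a day or two of injection, the excess in column 6 is 0 to 4%. Table 12 is also descriptive, with no planned comparison between columns. SAP 5.10 already derives time to onset from the vaccination that opens each window, AE and vaccination listings are planned (SAP 6.1), and the main safety tables do not use vaccination number. For eight patients, a careful reader could work out the timing by hand.

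Most of this stands, and it limits the point to presentation. It does not make the columns comparable: the documents give no ISR onset distribution, and a count with no denominator is what the reader will see.

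A reader might go further in three ways that the documents do not support.

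- **That the last column must rise, about fourfold.** This needs a constant onset rate and full completion. With drop-off, column 6 can fall below the others, and early stoppers put their long window in an earlier column.
- **That the last window for ISRs is effectively five years.** Table 12 belongs to the clinical study report, cut once all patients have withdrawn, died or completed the two-year visit; later data go to a supplemental report (SAP 5.14.4). Every related category in Protocol 9.2.4 also requires onset at a time related to administration, which limits remote events.
- **That the later first assessment after the last dose adds to the excess.** Protocol 7.3.1 does say "Two weeks after the patient has received their last vaccination they should be assessed for", against weekly checks earlier. But columns follow onset date, not visit date, and a longer gap would if anything miss brief reactions.

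**Conclusion.** The point holds as a matter of comparability. Table 12 uses windows of about 7 days before each patient's last vaccination and 30 days or more, with no stated end, after it (ratio about 4.3, range 3.1 to 5.8, to the End of Vaccination visit), and it omits the number vaccinated. Late-onset ISRs push up the column of each patient's last vaccination, and drop-off pushes the later columns down. Neither the net direction nor the size can be fixed from the documents. In the model, column 6 ranges from 0.68 to 1.76 times the mean of columns 1 to 5, depending on the assumed onset time and drop-off, with no true difference between doses. With early onset and full completion the distortion is negligible.

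The primary safety summaries are unaffected. This is a cheap improvement to one descriptive table, worth making because that table is the only dose-by-dose view of the main expected toxicity.

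**What to change.** In SAP 5.8.1 and 5.10:

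1. Count in columns 1 to 6 only ISRs with onset from the dose to day 7 after it, or to before the next dose if that is earlier.
2. Add a column for later events: 'onset more than 7 days after the most recent vaccination'.
3. Keep every ISR in Total.
4. Show the number of patients vaccinated under each numbered column.

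The time-to-onset variable in SAP 5.10 supplies what is needed. Two details should be settled in the same sentence. First, SAP 5.10 leaves onset time uncalculated when the AE start time is missing and a dosing time was entered, so the 7-day limit should use dates. Second, with doses exactly 7 days apart, an onset on day 7 goes to the next dose, so an inclusive day 7 gives a patient's last vaccination one calendar day more (days 0 to 7 against days 0 to 6).

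The cost is one extra column and one extra row, with no new data. The downside is that a few late ISRs leave the numbered columns, though they stay visible in their own column and in Total. The limit does not remove reactions to an earlier dose that start within 7 days of a later one; these are still charged to the later dose.
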